8.2.5 Multiplicity

Since there is only one primary PD hypothesis, no multiplicity adjustment will be made when testing the primary hypothesis. The secondary and tertiary PD hypotheses will only be tested if the primary PD hypothesis is met. There are six separate secondary hypotheses and more than 8 tertiary hypotheses. Benjamini and Hochberg's false discovery rate multiplicity

adjustment will be applied at a rate of 10% when testing the secondary and tertiary hypotheses.

8.2.6 Interim Analysis

There will be up to 3 interim analyses done for this study. The first interim analysis will be performed after the initial 9 RCC patients, randomized 2:1 to either receive neoadjuvant MK-3475 vs. control (proceed to SOC RCC resection), have all undergone tumor resection and the assessment of tumor immune cell infiltrates has been completed. At the first interim analysis, the number of patients with an immune cell infiltration “response”, defined as a 2-fold or greater increase in the immune cell infiltrate in RCC tumor specimens compared with that in the pretreatment tumor biopsy specimens from the same patient, will be examined in the 6 patients receiving neoadjuvant MK-3475. If 4 or more of the first 6 patients receiving neoadjuvant MK-3475 respond, randomization will continue 2:1 to receive either neoadjuvant MK-3475 or control (proceed to SOC RCC resection), respectively, for the remainder of the study. If less than 4 of the first 6 patients receiving neoadjuvant MK-3475 respond, all subsequently enrolled patients may receive neoadjuvant MK-3475 with no further patients being randomized to the control group. Further, if there are 0 or 1 responders in the first 6 patients receiving neoadjuvant MK-3475, then the number of doses of MK-3475 that will be administered in patients subsequently enrolled may be increased from two to three (with the 200 mg dose and the Q3W dosing interval remaining the same). The probabilities of various outcomes after the first interim analysis are provided in [Table 12](#) below, assuming a true immune cell infiltration response rate of 5%, 30%, or 70%.

Table 12 First Interim Analysis Outcome Scenarios

Various outcomes after the first interim analysis assuming a true immune cell infiltration response rate of 5%, 30%, or 70%

| Outcome of first interim analysis | Action | Probability if true response rate = | | |
|-----------------------------------|--|-------------------------------------|-----|-----|
| | | 5% | 30% | 70% |
| 0-1 responders | Enroll all subsequent patient to MK-3475, increase from 2 to 3 doses | 97% | 42% | 1% |
| 2-3 responders | Enroll all subsequent patient to MK-3475, continue with 2 doses | 3% | 51% | 24% |
| 4-6 responders | Continue 2:1 randomization (MK-3475:Control) | < 1% | 7% | 74% |

The second interim analysis will occur after a total of 18 RCC patients have undergone tumor resection, with either 15 receiving neoadjuvant MK-3475 with 3 controls or 12 receiving neoadjuvant MK-3475 with 6 controls. The primary PD hypothesis will be assessed, and success will be declared and enrollment may stop if there is at least 80% posterior probability that the true response rate is at least 30%. If success cannot be declared after the initial 18

patients, an additional 9 patients may be enrolled and randomized as determined by the results of the first interim analysis, and a third interim analysis will occur after 27 RCC patients have undergone tumor resection, with either 24 receiving neoadjuvant MK-3475 with 3 controls or 18 receiving neoadjuvant MK-3475 with 9 controls. The primary hypothesis will be assessed, and success will be declared and enrollment may stop if there is at least 70% posterior probability that the true response rate is at least 30%. If success cannot be declared after the initial 27 patients, an additional 9 patients may be enrolled and randomized as determined by the results of the first interim analysis. The final analysis will be performed after 36 RCC patients have undergone tumor resection. At the final analysis, success will be declared if there is at least 60% posterior probability that the true response rate is at least 30%.

After each interim analysis, decisions related to enrolling additional patients may deviate from the rules defined above based on the accumulating data, at the discretion of the Sponsor.

In addition, decisions related to stopping the study for futility may also be considered at each interim analysis. At the second interim analysis, if there are only 0 or 1 responders the study may be stopped for futility. The probability of this happening when the true response rate is 30% is 8.5% (3.5%) with a sample size of 12 (15). At the third interim analysis, if there are 2 or less responders the study may be stopped for futility. The probability of this happening when the true response rate is 30% is 6.0% (1.2%) with a sample size of 18 (24).

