The interim analyses will include re-estimations of the sample size required to maintain power in the trial. If results of the interim analyses indicate that a larger sample size is necessary, subject enrollment may be extended. Details are described in Section 8.0 – Statistical Analysis Plan. If further extension of enrollment beyond the 36 subjects proposed in this protocol is needed, a protocol amendment will be filed.

Results of the first interim analysis will be used to determine if subsequent patients recruited to participate in the study will continue to be randomized to the untreated control group that does not receive neoadjuvant MK-3475 or whether subsequent patients enrolled in the study will all receive neoadjuvant MK-3475. This determination will be made according to the pre-specified algorithm described in detail in Section 8.0 - Statistical Analysis Plan.

Results from the first interim analysis will also be used to determine if the two dose regimen for neoadjuvant MK-3475 should be increased to 3 doses, according to the pre-specified algorithm described in detail in Section 8.0 – Statistical Analysis Plan.

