It is also highly likely that a period of time of at least 5-6 weeks will be necessary for MK-3475 to stimulate an anti-tumor response that manifests as an immune cell infiltration of the primary tumor. In a study in patients with metastatic melanoma, significant increases in CD8+ T cell infiltrates were observed in tumor biopsies collected after 3-8 weeks of MK-3475 therapy in the majority of patients who responded clinically to therapy [71]. Importantly, in four of five patients with delayed clinical responses to therapy, increases in tumor TIL's were not observed in tumor biopsies collected 3-8 weeks following initiation of MK-3475 therapy but were later observed in biopsies collected 80-120+ days following treatment initiation. The variability of the time interval between the initiation of MK-3475 therapy and tumor biopsy in that melanoma study precludes a precise estimation of length of time needed for MK-3475 to augment anti-tumor responses and stimulate infiltration of the tumor with immune cells. We anticipate that immunologically, the tumor, present during this period of neoadjuvant therapy with MK-3475, will serve as an important source of both RCC antigen-specific T cells and tumor antigens for stimulating anti-tumor immune responses in this setting, and that without the presence of the tumor, MK-3475 might not be able to stimulate an effective anti-tumor immune response. As discussed in Section 8.2.6 (Interim Analysis), if at least a 2-fold increase in immune cell infiltrates is not seen in more than one

of the first 6 subjects that receive 2 Q3W doses of MK-3475, we may increase to three the number of Q3W doses that subsequent subjects receive, primarily to allow more time for the tumor to be exposed to MK-3475 and therefore facilitate the stimulation of anti-tumor immunity and immune cell infiltration of the primary tumor.

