5.3 Randomization or Treatment Allocation

Subjects will be assigned randomly according to a computer-generated allocation schedule.

The sample allocation schedule is shown in [Table 4](#).

Table 4 Sample Allocation Schedule

| Patients ^a | Treatment Group |
|-----------------------|--|
| n=24 | 200 mg MK-3475 Q3 weeks, 2 or 3 doses ^b |
| n=12 | Control |

^a Patients will be randomized to receive neoadjuvant MK-3475 or control. Allocation will be done in blocks of 3, ensuring 6 treated and 3 controls will be available for the first interim analysis. Depending on results of the first interim analysis, the control arm (and allocation numbers associated with the control arm) may be dropped from the allocation schedule, in which case patient numbers will be 33 and 3 for MK-3475 and controls, respectively.

^b Also depending on the results of the first interim analysis, the number of neoadjuvant doses of MK-3475 may be increased from 2 to 3.

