8.2.3 Approaches to Analyses

The following populations are defined for the analysis and reporting of data. All subjects will be reported, and their data analyzed, according to the treatment(s) they actually received.

All Subjects as Treated (AST) - All subjects who received at least one dose of the investigational drug. This population will be used for assessments of safety and tolerability.

Per-Protocol (PP) – The set of data generated by the subset of subjects who comply with the protocol sufficiently to ensure that these data will be likely to exhibit the effects of treatment, according to the underlying scientific model. Compliance covers such considerations as exposure to treatment, availability of measurements and absence of major protocol violations. Major protocol violators will be identified to the extent possible by individuals responsible for data collection/compliance, and its analysis and interpretation. Any subjects or data values excluded from analysis will be identified, along with their reason for exclusion, in the Results Memo for this study. At the end of the study, all subjects who are compliant with the study procedure as aforementioned and have available data

from at least one treatment will be included in the primary analysis dataset. This population will be used for the all PD analyses.

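### If the number of doses changes after the first interim analysis, the primary posterior pools two-dose and three-dose patients under one rate, and no posterior for the three-dose patients is planned

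*Combined protocol and SAP*

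**What the plan says.** Section 8.2.6 examines six treated patients at the first interim analysis (IA1). With fewer than 4 responders, the control arm may be dropped. With 0 or 1, "then the number of doses of MK-3475 that will be administered in patients subsequently enrolled may be increased from two to three". Section 4.2.2.4 gives the reason for that change: "primarily to allow more time for the tumor to be exposed to MK-3475 and therefore facilitate the stimulation of anti-tumor immunity".

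The counts do not separate the two regimens:

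- Table 4 (Section 5.3) has a single treated group, "200 mg MK-3475 Q3 weeks, 2 or 3 doses". If controls are dropped, "in which case patient numbers will be 33 and 3 for MK-3475 and controls, respectively".
- Section 8.2.6 gives 15 or 12 treated patients at the second interim analysis (IA2). At the third (IA3) it continues "with either 24 receiving neoadjuvant MK-3475 with 3 controls or 18 receiving neoadjuvant MK-3475 with 9 controls".
- Section 8.2.7 gives success cut-offs of 7 of 15, 9 of 24 and 11 of 33 on the branch without further controls. The futility triggers in 8.2.6 are at most 1 responder at IA2 and at most 2 at IA3.
- The model in 8.2.4 has one response rate and a Beta(0.1, 0.1) prior. Its only sensitivity analysis varies the definition of a responder.

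Three other statements come near the point without settling it. Section 8.2.3 says "All subjects will be reported, and their data analyzed, according to the treatment(s) they actually received", but not whether two-dose and three-dose courses are different treatments. Section 2.1 says "The interim analyses will include re-estimations of the sample size required to maintain power in the trial", but not which patients that would use. Section 8.2.6 adds that "decisions related to enrolling additional patients may deviate from the rules defined above based on the accumulating data".

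**The concern.** The totals 15, 24 and 33 are 6 + 9, 6 + 18 and 6 + 27. After a change in the number of doses, the first six are two-dose patients who, by the trigger itself, contributed at most one response. The rest had the other regimen. One rate is fitted to both groups although the change is made in the expectation that they may differ.

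Two things follow. The primary posterior can fall short because of patients from the replaced regimen, and no planned result shows what the three-dose patients achieved. The power and futility figures that a reader would consult also do not describe this branch. The branch is not remote: Table 12 gives it 97% probability at a 5% rate and 42% at 30%. Under 8.2.5, missing the primary hypothesis also means the secondary and tertiary hypotheses are not tested.

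**Working it through.** **Inputs.** Beta(0.1, 0.1) prior and 30% target (8.2.4); treated totals (5.3, 8.2.6); thresholds of 80%, 70% and 60% at IA2, IA3 and the final analysis (8.2.6); 36 subjects; rules applied mechanically. Sections 8.1 and 8.2.4 attach the same thresholds to IA1, IA2 and IA3. The 8.2.6 version is used because it matches Table 14 and, with one exception, the cut-offs in 8.2.7. The exception is the printed 6 of 24, whose posterior is 27.6%; 8 of 24 (62.4%) is needed and is used here. That cut-off is on the branch that keeps controls.

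**Formula.** For x responders of n, posterior = P(rate ≥ 0.30) under Beta(0.1 + x, 0.1 + n − x). A cut-off is the smallest x that reaches the threshold.

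**Reproducing the plan.** The pooled cut-offs reproduce: 7 of 15 gives 90.9% (6 gives 78.5%), 9 of 24 gives 77.5% (8 gives 62.4%), and 11 of 33 gives 64.9% (10 gives 50.1%). Exact enumeration over IA1 outcomes, with one rate for everyone and the first six kept in, gives end-of-study success of 84.8% at a 40% rate and 44.1% at 30%. Table 14 prints 84.8% and 44.0%; every cell is within 1 point. So Table 14 rests on pooling and one rate.

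**What the pooled cut-offs require of three-dose patients (no rate assumed).** Subtract the IA1 responders from 7, 9 and 11:

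| Analysis | Needed after 0/6 | Three-dose-only posterior | Needed after 1/6 | Three-dose-only posterior | Threshold |
|---|---|---|---|---|---|
| IA2 | 7 of 9 | 99.9% | 6 of 9 | 98.9% | 80% |
| IA3 | 9 of 18 | 96.1% | 8 of 18 | 89.8% | 70% |
| Final | 11 of 27 | 87.7% | 10 of 27 | 77.5% | 60% |

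One responder fewer at the end fails on 10 of 33 (50.1%). The three-dose patients alone then give 77.5% (10 of 27, after 0/6) or 63.3% (9 of 27, after 1/6).

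**Table 14 split by IA1 outcome, common rate 40%.**

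| IA1 responders | Probability | End-of-study success |
|---|---|---|
| 0–1 | 23.3% | 67.5% (55.2% after 0, 70.6% after 1) |
| 2–3 | 58.8% | 87.6% |
| 4–6 | 17.9% | 98.2% |

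Check: 0.233 × 67.5 + 0.588 × 87.6 + 0.179 × 98.2 = 84.8%.

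**Futility triggers, three-dose rate 30%.** The quoted figures are P(≤1 of 15) = 3.5% and P(≤2 of 24) = 1.2%. Given the IA1 result they become:

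- IA2: P(≤1 of 9) = 19.6% after 0/6; P(0 of 9) = 4.0% after 1/6.
- IA3: P(≤2 of 18) = 6.0% after 0/6; P(≤1 of 18) = 1.4% after 1/6.

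These are chances of meeting a non-binding trigger, not of stopping.

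**The case against.** Pooling fits the hypothesis. Sections 3.1 and 8.2.1 ask about neoadjuvant MK-3475 in general, and Table 4 openly defines one group. Nothing in the documents contradicts pooling. If the two rates are equal, the first six are valid data, and dropping them only when they are unfavourable is what would bias the result. This stands, and it is why pooling should remain primary.

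A reader might infer that Table 14 is wrong, or that real power is far below 85%. With an assumed two-dose rate of 5% and three-dose rate of 40%, whole-trial success is 57.0%. But Table 14 assumes one rate per row and is right on that basis. After a switch that pair averages (6 × 5% + 27 × 40%) / 33 = 33.6%, and Table 14 gives 44.0% at 30% and 67.5% at 35%, so 57.0% is what such a mixture should yield. The documents give no rate by number of doses; Section 4.2.2.4 supports a direction, not a size. The 57.0% is therefore an illustration, not a finding.

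The dose change is optional, enrolment may depart from the rules at the Sponsor's discretion, and futility stopping is not binding. That makes the branch conditional but does not define its analysis. The secondary and tertiary hypotheses are largely blacked out, so the loss from not testing them cannot be sized.

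**Conclusion.** The point holds as a gap in interpretation on a planned branch. After 0 or 1 of 6 and a change in the number of doses, the primary posterior describes a mixture of regimens, and no result for the three-dose patients is specified. The rate-free size is a final 10 of 27 after 0 of 6: 50.1% pooled (fail) against 77.5%. On the same branch, success at a common 40% is 67.5% against the 84.8% averaged over all IA1 outcomes. The IA2 futility trigger at a three-dose rate of 30% is met 19.6% of the time after 0 of 6, against the quoted 3.5%; after 1 of 6 it is 4.0%.

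Two stronger readings are not supported. Pooling does not create a false claim: the selected first six can only make success harder to reach. Nor do the documents show that a three-dose-only test ought to replace the pooled one. The figures assume 36 subjects, mechanical use of the rules, and the thresholds as placed in 8.2.6.

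**What to change.** Keep the pooled posterior as primary. In 8.2.6 add:

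> If the number of doses is changed after IA1, the posterior probability of a response rate of 30% or more will also be calculated from the three-dose patients alone and reported, as supportive, beside the pooled posterior at each later analysis.

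In 8.2.7, state that Table 14 and the futility probabilities assume one rate across regimens. Add the success and futility-trigger probabilities after 0 of 6 and after 1 of 6. Reconcile the 80/70/60% thresholds in 8.1 and 8.2.4 with those in 8.2.6. If IA1 has already taken place, list and explain the change as Section 8.2 provides.

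The cost is one extra calculation per analysis, a few table rows and a less favourable stated power on this branch. No patients are added, and the primary decision rule keeps its operating characteristics. The supportive posterior must not replace the primary: at a common rate of 20%, using three-dose patients only after a switch, at unchanged thresholds and without an IA2 look, would raise whole-trial success from 7.0% to 11.2%. No view is taken on the number of doses.

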8.2.7 Power

Primary Safety: If a serious (Grade 3 or Grade 4) adverse experience occurs at a rate of 1%, 5% or 10% then the chance of observing such an adverse event among the various possible sample sizes are provided in [Table 13](#).

Table 13 Probability of Observing Serious Grade 3 or Grade 4 Adverse Experience for Various AE Rates

| Serious AE Rate | Probability (%) of observing serious AE among MK-3475 treated patients | | | | |
|-----------------|--|---------------|---------------|---------------|---------------|
| | $n_{MK} = 12$ | $n_{MK} = 15$ | $n_{MK} = 18$ | $n_{MK} = 24$ | $n_{MK} = 33$ |
| 1% | 11 | 14 | 17 | 21 | 28 |
| 5% | 46 | 54 | 60 | 71 | 82 |
| 10% | 72 | 79 | 85 | 92 | 97 |

n_{MK} = final number of patients receiving neoadjuvant MK-3475

If no AE of a given type is observed in any subject receiving neoadjuvant MK-3475, then the true incidence of the adverse experience at that dose is at most 13%, 10%, 9%, 6%, or 5% with 80% confidence when the sample size among those receiving neoadjuvant MK-3475 is 12, 15, 18, 24 or 33, respectively.

Primary PD:

Table 14 shows the cumulative probabilities of stopping and declaring success on the primary PD hypothesis after each interim analysis assuming various true immune cell infiltration response rates and implementing the interim analysis strategy as described in Section 8.2.6. If the true immune infiltration response rate is 40%, there is ~85% power to meet the primary hypothesis at either the second or third interim analysis, or at the end of the study. If the true response rate is 45%, there is ~85% to meet the primary hypothesis at either the second or third interim analysis. To have high power (>80%) to meet the primary hypothesis after the second interim analysis, the true response rate must be greater than or equal to 55%.

Table 14 Cumulative Probabilities of Stopping and Declaring Success After Each Interim Analysis Assuming Various True Immune Cell Infiltration Response Rates

| True immune cell infiltration response rate | Probability (%) of stopping and declaring success (obtaining stated level of posterior probability that the true immune cell infiltration response rate of MK-3475 at least 30%) | | |
|---|--|------------|-----------------|
| | After IA 2 | After IA 3 | At end of study |
| 5% | <0.1 | <0.1 | <0.1 |
| 10% | <0.1 | <0.1 | 0.1 |
| 15% | 0.3 | 0.7 | 1.0 |
| 20% | 1.7 | 4.3 | 6.6 |
| 25% | 6.3 | 14.4 | 22.0 |
| 30% | 13.0 | 29.4 | 44.0 |

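### The futility probabilities of 8.5% (n=12) and 6.0% (n=18) leave out the interim-1 rule; when that rule is followed, both are 0%.

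*Combined protocol and SAP*

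**What the plan says.** Section 8.2.6 sets allocation after the first interim from the first six treated patients. "If 4 or more of the first 6 patients receiving neoadjuvant MK-3475 respond, randomization will continue 2:1"; with fewer than 4 responders, all later patients may receive MK-3475. Table 12 gives the matching actions: everyone to MK-3475 after 0–1 or 2–3 responders, and continued 2:1 after 4–6.

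The second interim then has 12 treated with 6 controls, or 15 treated with 3 controls. The third has 18 treated with 9 controls, or 24 with 3. Allocation after the second interim still follows the first: "an additional 9 patients may be enrolled and randomized as determined by the results of the first interim analysis".

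The futility limits are in the same section:

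- Second interim: "At the second interim analysis, if there are only 0 or 1 responders the study may be stopped for futility". The plan then attaches one figure to each possible number of treated patients: "The probability of this happening when the true response rate is 30% is 8.5% (3.5%) with a sample size of 12 (15").
- Third interim: "At the third interim analysis, if there are 2 or less responders the study may be stopped for futility". At the same 30% rate the probability "is 6.0% (1.2%) with a sample size of 18 (24").

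The section also lets the Sponsor depart from the plan: "decisions related to enrolling additional patients may deviate from the rules defined above". Section 8.2.7 says that Table 14 was computed "implementing the interim analysis strategy as described in Section 8.2.6".

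**The concern.** The sample sizes 12 and 18 are outcomes of the interim-1 decision. Under the rule, a trial with 12 treated patients at the second interim has already recorded at least 4 responders among its first 6. Responder counts cannot fall, so neither the limit of 1 nor the limit of 2 can be met on that branch. The 8.5% and 6.0% nevertheless appear without any note that they leave this out.

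A reader would conclude that the 2:1 branch carries more than twice the second-interim false-futility risk of the all-treated branch (8.5% against 3.5%). Under the rule, that branch carries none and the all-treated branch carries the whole 3.5%. The futility figures also rest on a different basis from Table 14, which is said to implement the interim strategy.

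**Working it through.** **Inputs (section 8.2.6 and Table 12).** True response rate p = 0.30. Futility limits: ≤1 responder at the second interim, ≤2 at the third. Treated patients: 6 at the first interim, then 12 and 18 (2:1 kept) or 15 and 24 (controls dropped). Branch rule: at least 4 of 6 keeps 2:1; fewer than 4 drops controls.

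**Step 1: reproduce the printed figures.** With X ~ Bin(n, 0.3):

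- n=12: P(X≤1) = 0.7¹² + 12·0.3·0.7¹¹ = 8.50% (printed 8.5%)
- n=15: P(X≤1) = 0.7¹⁵ + 15·0.3·0.7¹⁴ = 3.53% (printed 3.5%)
- n=18: P(X≤2) = 0.7¹⁸ + 18·0.3·0.7¹⁷ + 153·0.3²·0.7¹⁶ = 6.00% (printed 6.0%)
- n=24: P(X≤2) = 0.7²⁴ + 24·0.3·0.7²³ + 276·0.3²·0.7²² = 1.19% (printed 1.2%)

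All four are fixed-n tails that take no account of how each sample size is reached.

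**Step 2: branch probabilities.** Let x₆ be the responders among the first six treated. P(x₆≥4) = 15·0.3⁴·0.7² + 6·0.3⁵·0.7 + 0.3⁶ = 7.05%, so P(x₆<4) = 92.95%. Table 12 gives 7% and 42% + 51% = 93%.

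**Step 3: apply the rule.**

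| Treated n | Condition | Whole-design probability | Given the branch | Printed |
|---|---|---|---|---|
| 12 | ≤1 responder and x₆≥4 | 0% | 0% | 8.5% |
| 18 | ≤2 responders and x₆≥4 | 0% | 0% | 6.0% |
| 15 | ≤1 responder and x₆<4 | 3.53% | 3.53/0.9295 = 3.79% | 3.5% |
| 24 | ≤2 responders and x₆<4 | 1.19% | 1.19/0.9295 = 1.28% | 1.2% |

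The zeros hold at any true response rate, because the events exclude each other. The n=15 and n=24 values are unaffected, because having ≤1 of 15 or ≤2 of 24 already implies fewer than 4 of the first six. The n=24 value takes no account of futility stops at the second interim.

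**Step 4: when the printed figures would apply.** If 2:1 were kept whatever interim 1 shows, 8.5% and 6.0% are exact. If it were kept by discretion after fewer than 4 of 6 responded, they become 8.50/0.9295 = 9.1% and 6.00/0.9295 = 6.4%.

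**Step 5: compare with Table 14.** Cumulative success (%) after the second / third interim, using success thresholds recomputed from the beta prior, 6/12, 7/15, 7/18 and 9/24:

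| True rate | Printed | Branching by rule | Always 2:1 | Always all treated |
|---|---|---|---|---|
| 40% | 39.2 / 69.3 | 39.1 / 68.7 | 33.5 / 63.4 | 39.0 / 68.6 |
| 55% | 82.0 / 97.5 | 81.3 / 97.4 | 73.9 / 94.8 | 81.8 / 97.5 |

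Table 14 is not compatible with always keeping 2:1, the basis on which 8.5% and 6.0% are exact. The table alone does not separate branching from always treating everyone; the statement in section 8.2.7 does that.

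**The case against.** The strongest reply is that the printed figures contain no slip of calculation. Each is the correct tail for its stated sample size, and the sentence can be read as a statement about fixed n. Section 8.2.7 lists its success thresholds by sample size in the same way.

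The interim-1 rule is also not binding. Dropping controls is worded as *may* in section 8.2.6 and in the notes to Figure 1 and Table 4; Table 4 itself shows 24 treated and 12 controls, the 2:1 schedule kept throughout; and the Sponsor's freedom to deviate is stated just before the futility paragraph. A permitted departure is the one way to meet the futility limit at n=12 or n=18, and there the printed figures are right or close (9.1% and 6.4% in the discretionary case). Finally, the figures overstate the risk of a futility stop that is itself optional.

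Most of this stands as a limit on the point. It explains where the numbers come from and shows that little depends on them. It does not remove the defect: the text does not present 8.5% and 6.0% as deviation scenarios or as leaving out the interim-1 rule, and Table 12 lists all-MK-3475 enrolment as the action for 0 to 3 responders. The objection does favour keeping the figures with a condition attached over deleting them.

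**Conclusion.** The point holds. With the interim-1 rule followed, the probability of meeting the futility criterion on the 2:1 branch is 0% at both later interims, against the stated 8.5% and 6.0%. The 3.5% and 1.2% need no change as whole-design values.

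The zeros assume that the rule is followed and that the responders counted at interim 1 remain in the later counts. The 3.5% and 1.2% also assume one 30% response rate for the 2- and 3-dose regimens, since the number of doses may change after interim 1.

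Severity is low. Futility stopping is non-binding, the 2:1 branch has about 7% probability at a 30% rate, and no threshold or sample size rests on the two figures.

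**What to change.** Amend the two probability sentences in section 8.2.6 in one of two ways:

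- Replace 8.5% and 6.0% with 0%, adding that the futility criterion cannot be met on the 2:1 branch when the interim-1 rule is followed; or
- Keep 8.5% and 6.0%, adding that they apply only if 2:1 randomisation is kept regardless of the interim-1 result. This version preserves the figures relevant to a Sponsor departure.

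In either case, keep 3.5% and 1.2% and label them as whole-design probabilities of meeting the criterion.

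Optionally, add a cumulative figure for the case where the study always stops once the second-interim criterion is met. The third interim then adds P(2 of 15, then 0 of 9) = 0.37%, giving 3.53% + 0.37% = 3.90%. That figure needs its own label, because it assumes a binding stop, which the plan does not have, and one 30% rate for both regimens.

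The futility rule itself stays in force on both branches. The cost is SAP wording only.
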